4.7.2. Study Intervention Compliance

Study intervention compliance will be assessed by the compliance rate. The compliance rate is defined as (total amount of drug dosage injected or taken) / (total amount of drug dosage planned to be injected or taken during the study). The compliance rate will be summarized using descriptive statistics (n, mean, SD, median, Q1, Q3, min, max) by study intervention and cohort based on the FAS.

4.7.3. Adverse Events (AEs)

For analysis purposes, AEs will be classified as pre-treatment AEs, TEAEs, and post-TE AEs, defined as follows:

- Pre-treatment AE: defined as any AEs that started after informed consent was signed and prior to the administration of the study intervention.
- TEAE: defined as any AEs reported with an onset date on or after the first dose of study intervention(s) until the end of TE Period.
- Post-TE AE: defined as any AEs with onset after the TE Period through the end of Follow-Up Period.

All AEs will be coded using MedDRA version 25.0 and later.

For AEs with completely missing or partially missing start/stop dates, if it can't be decided whether the AE is TEAE due to the missing dates, the AE will be classified as TEAE. Imputation rules for missing or partial missing dates of AEs are described in [Appendix 4](#).

An overview table of all TEAEs by cohort and overall will be summarized in the following categories:

- Number of TEAEs (total number of TEAEs only)
- Participants with any TEAEs
- Participants with TEAEs by strongest relationship to study intervention(s)
- Participants with TEAEs by maximum severity
- Participants with TEAEs leading to any study intervention discontinuation
- Participants with TEAEs leading to any study intervention interruption
- Participants with TEAEs leading to PEG-IFNa and TDF/TD dose reduction
- Participants with study intervention-related TEAEs
- Participants with Grade 3/4/5 TEAEs
- Participants with serious TEAEs
- Participants with study intervention-related serious TEAEs
- Participants with TEAE leading to death

The following summary tables of TEAEs will be presented by MedDRA SOC and PT using the number and percentage of participants by cohort and overall:

- TEAEs
- Study intervention related TEAEs
- TEAEs by maximum severity
- Serious TEAEs

In addition, the following TEAE tables will also be summarized by MedDRA PT only for each cohort and overall:

- TEAEs
- Study intervention related TEAEs
- Serious TEAEs

A participant with multiple occurrences of the same AE will be counted only once, at the maximum severity (toxicity grade) or strongest relationship to study intervention.

A TEAE table of injection site reactions will be summarized by MedDRA PT for each cohort and overall in order of descending incidence.

The following table-listings will be presented per cohort based on the All Enrolled Set:

- SAEs
- AEs leading to study intervention interruption
- AEs leading to study intervention discontinuation
- AEs leading to death

All AEs will be presented in a by-participant listing based on the All Enrolled Set. In addition, the local tolerability of VIR-3434 will also be listed.

4.7.4. Clinical Laboratory

All statistical analyses of laboratory values will be performed using conventional units. Clinical laboratory data collected will be summarized using quantitative methods.

4.7.4.1. Summaries of Laboratory Results

For the laboratory measurements, the observed values and change from baseline values of the continuous variables of liver function tests, hematology, serum chemistry, and coagulation will be summarized using descriptive statistics (n, mean, SD, median, Q1, Q3, min, max) by cohort at each scheduled visit until EOS.

Separate listings containing individual participant liver function tests, hematology, chemistry, coagulation, and urinalysis values will be provided by participant ID and visit in chronological order, including data collected from both scheduled and unscheduled visits. Values falling out of the relevant normal range (between the value of lower limit of normal (LLN) and upper limit of normal (ULN)) and having a severity grade of 1 or higher on laboratory abnormalities will be flagged as appropriate. Local lab data will be presented only in a by-participant listing and will be flagged accordingly.

In addition, results of positive urine/serum pregnancy test will be listed in the individual participant data listing only.

4.7.4.2. Summaries of Laboratory Abnormalities

The Common Terminology Criteria for Adverse Events (CTCAE) v5.0 (CTCAE 5.0 2017) will be used as the reference on the grading scale to assign severity (toxicity) grades (1 to 4) to abnormal results for the laboratory parameters of interest, as shown in [Appendix 5](#). Grade 0 refers to the normal values that do not meet the criteria of laboratory abnormalities. Grade 5 refers to death related to an adverse event, if any.

For the laboratory abnormalities, the number and percentage of participants who met at least 1 threshold criterion of severity grade during the TE Period will be summarized by cohort based on the most severe post-baseline abnormality for selected laboratory parameters in [Appendix 5](#).

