9.4.5. Missing Data

Values for missing safety laboratory data will not be imputed. However, a missing baseline result (defined as predose Day 1) will be replaced with a screening result, if available.

[figure not shown]
If no pre-treatment laboratory value is available, the baseline value will be assumed to be normal (ie, no grade [Grade 0]) for the summary of graded laboratory abnormalities. If safety laboratory results for a participant are missing for any reason at a time point, the participant will be excluded from the calculation of summary statistics for that time point.

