1.2. Study Design

1.2.1. Overall Design

STRIVE is a Phase 2, multi-center, open-label study designed to evaluate the safety and efficacy of regimens containing VIR-3434, VIR-2218, PEG-IFN α , and NRTI (TDF/TD)¹ in non-cirrhotic adult participants with chronic HBV infection who have not received prior NRTI or PEG-IFN α treatment. The study is planned to be conducted at multiple clinical investigative sites globally.

The STRIVE sub-study is intended to evaluate up to 48-week regimens of VIR-3434 and NRTI, VIR-3434 and NRTI in combination with VIR-2218, and VIR-3434 and NRTI in combination with both VIR-2218 and PEG-IFN α in participants with chronic HBV infection. Study populations II and III in [Table 2](#) as defined in the Master Protocol will be included in this sub-study. Participants who have not received any prior NRTI treatment will be eligible for enrollment into this sub-study.

Table 2: Study Population

Master Protocol Population	HBeAg Status	HBV DNA Level	ALT Level
II	Positive	> 2,000 IU/mL	> ULN and $\leq 5 \times$ ULN

¹ In STRIVE, NRTI refers to Tenofovir disoproxil fumarate dose (TDF) or Tenofovir disoproxil (TD). TDF will be supplied in the United States, TD will be supplied outside the United States.

III	Negative	> 2,000 IU/mL	> ULN and \leq 5x ULN
-----	----------	---------------	-------------------------

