4.7.5. Summaries of Events of Clinical Interest

The TE laboratory events of clinical interest (ECI) are defined as instances of:

- ALT > 5 x ULN and > 2 x baseline.

The number and percentage of participants with ECI will be summarized for each scheduled visit until EOS by cohort. If any participant has multiple ECIs, they will only be counted once. An ECI is considered resolved when ALT returns to \leq Day 1 baseline value.

A listing including individual participant ECI data will be provided.

If a participant has at least one ECI, the related data – substance use, exercise, and travel history – will be collected, and the corresponding listings will be presented. Otherwise, if no participant meets the ECI criteria, the three listings will not be provided, as no data will have been collected.

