APPENDIX 5. SEVERITY (TOXICITY) GRADES FOR LABORATORY ABNORMALITIES

Below parameters' toxicity grades will be assessed and based on the Common Terminology Criteria for Adverse Events (CTCAE) v5.0 (CTCAE 5.0 2017).

Parameter	Parameter Code	CTCAE 5.0 Term
Liver Function Tests		
Alanine Aminotransferase	ALT	Alanine aminotransferase increased
Aspartate Aminotransferase	AST	Aspartate aminotransferase increased
Alkaline Phosphatase	ALP	Alkaline phosphatase increased
Total Bilirubin	BILI	Blood bilirubin increased
Chemistry		
Albumin	ALB	Hypoalbuminemia
Gamma Glutamyl Transferase	GGT	GGT increased
Creatinine	CREAT	Creatinine increased
Calcium	CA	Hypercalcemia Hypocalcemia
Bicarbonate	BICARB	Blood bicarbonate decreased
Sodium	SODIUM	Hypernatremia Hyponatremia
Lactate dehydrogenase	LDH	Blood lactate dehydrogenase increased
Potassium	K	Hyperkalemia Hypokalemia
Glucose	GLUC	Hyperglycemia Hypoglycemia
Hematology		
Hemoglobin	HCB1	Anemia Hemoglobin increased
Neutrophil	NEUT	Neutrophil count decreased
Lymphocytes (absolute)	LYM	Lymphocyte count decreased Lymphocyte count increased
Platelets decrease	PLAT1	Platelet count decreased
Coagulation		
International Normalized Ratio/ Prothrombin time	INR	INR increased

REFERENCES

Guidance on treatment endpoints and study design for clinical trials aiming to achieve cure in chronic hepatitis B and D: Report from the 2022 AASLD-EASL HBV-HDV Treatment Endpoints Conference. Ghany, Marc G. et al. *Journal of Hepatology*, Volume 79, Issue 5, 1254 – 1269.

FDA. Chronic Hepatitis B Virus Infection: Developing Drugs for Treatment.
<https://www.fda.gov/media/117977/download>. Apr 2022.

National Cancer Institute. Common Terminology Criteria for Adverse Events (CTCAE). 2017 November. Accessed 2018 October 01.
https://ctep.cancer.gov/protocoldevelopment/electronic_applications/docs/ctcae_v5_quick_reference_5x7.pdf

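### SAP 4.7.4.2 counts the worst post-baseline laboratory grade without requiring it to be worse than baseline, and plans no shift table

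*SAP*

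**What the plan says.** The SAP supplied is for the STRIVE sub-study. Its section 4.7.4.2 reports "the number and percentage of participants who met at least 1 threshold criterion of severity grade during the TE Period". The section goes on to specify which value decides each participant's grade: results "will be summarized by cohort based on the most severe post-baseline abnormality for selected laboratory parameters in" the SAP's Appendix 5. For the grading itself, CTCAE v5.0 "will be used as the reference on the grading scale to assign severity (toxicity) grades (1 to 4) to abnormal results for the laboratory parameters". The section adds that "Grade 0 refers to the normal values that do not meet the criteria of laboratory abnormalities". Appendix 5 repeats that "toxicity grades will be assessed and based on the Common Terminology Criteria for Adverse Events (CTCAE) v5.0" and lists parameters with their CTCAE terms. Neither place prints a cut-off, says how a participant who is abnormal at baseline is graded, or plans a cross-tabulation of baseline grade against worst grade.

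Section 1.2.1 (Table 2) sets the ALT entry range at "> ULN and \leq 5x ULN" for both enrolled populations. Section 4.1 leaves baseline missing when no pre-dose value exists, with no separate rule for grading.

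Some other ALT outputs do use baseline. Section 4.7.4.1 gives change from baseline at each visit. Section 4.7.5 defines the event of clinical interest (ECI) as "ALT > 5 x ULN and > 2 x baseline".

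**The concern.** A count headed by severity grade in the treatment-emergent (TE) period is naturally read as what happened on treatment. Under this rule it mixes new abnormalities with those the participant brought into the study. A participant with mild anaemia or raised GGT at Day 1 who stays at that level is counted just like one who develops it on drug, if that parameter is graded on absolute limits.

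The question is sharpest for ALT, since every STRIVE participant must be above ULN to enter. If ALT grades are multiples of ULN, the any-grade ALT row would be close to saturated and would say little about the regimens. If grades are taken relative to an abnormal baseline, the problem is much smaller, but then baseline is part of the derivation and 4.7.4.2 should say so.

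**Working it through.** The plan states no figure for this table, so there is nothing to reproduce. The check asks how much the count depends on the unstated grading anchor.

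**From the SAP.** Entry ALT is above 1x and at most 5x ULN (1.2.1, Table 2). The number of post-baseline liver-test visits in the Treatment Period comes from Appendix 2:
- Cohorts 1a and 2a: Day 8 plus Weeks 4 to 44, 1 + 11 = 12.
- Cohort 4a: Days 2 and 8 plus Weeks 4 to 44, 2 + 11 = 13.
- Cohort 5a: Days 2 and 8 plus Weeks 4 to 48, 2 + 12 = 14.

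The TE period runs at least 24 weeks beyond the last VIR-3434 dose (4.1), so 14 is not an upper limit for participants who stay in follow-up.

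**Assumed, not in the documents.** True ALT is log-uniform on 1-5x ULN. Within-person SD on the log scale is 0.1, 0.2 or 0.3. There is no drug effect. Participants are kept if the observed baseline is above 1x and at most 5x ULN. ULN-based grades use cut-points 1, 3, 5 and 20x ULN. Baseline-anchored grading uses an illustrative lowest cut-off of 1.5x the observed baseline.

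**Model.** For participant i and sample j, ALT(i,j) = T(i) x exp(e(i,j)), with e normal, mean 0 and SD s. The worst value is W(i) = max over j of ALT(i,j), and B(i) is the observed baseline. Simulated participants: 200,000 before the entry filter.

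| s | Samples | W > ULN | W > 3x ULN | Worst grade above baseline grade | W ≥ 1.5x B |
|---|---|---|---|---|---|
| 0.1 | 1 | 98% | 31% | 5.6% | 0.2% |
| 0.2 | 1 | 96% | 30% | 11% | 7% |
| 0.3 | 1 | 94% | 30% | 17% | 16% |
| 0.1 | 14 | 100% | 42% | 20% | 2% |
| 0.2 | 14 | 100% | 53% | 40% | 38% |
| 0.3 | 14 | 100% | 65% | 57% | 63% |

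**With ALT falling on treatment.** A second simulation uses 12 visits and a 28-day half-time towards a lower plateau. Ranges are over s = 0.1 to 0.3.

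| ALT course | W > ULN | W > 3x ULN | W > 1.5x B |
|---|---|---|---|
| Unchanged | 100% | 41-64% | 2-60% |
| Falls to 50% of baseline | 95-97% | 25-33% | 0-15% |
| Falls to 25% of baseline | 92% | 22-24% | 0-10% |

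Under ULN anchoring, the any-grade count barely moves when ALT improves greatly (100% to 92%). The count above 3x ULN does respond to the ALT course. Under baseline anchoring, the any-grade count is neither saturated nor insensitive.

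**What the ECI leaves uncovered.** A rise from 1.2x to 4.9x ULN is 4.9 / 1.2 = 4.1-fold but stays below 5x ULN. A rise from 4x to 7.9x ULN is 7.9 / 4 = 1.98-fold, below the 2x baseline condition. Neither is an ECI.

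**The case against.** The strongest objection is that the anchor is unknown. A reader might infer that nearly every STRIVE participant will be tabulated with an ALT abnormality whatever the drugs do. The documents do not support that. The SAP defers to CTCAE v5.0 and prints no thresholds, so grading on multiples of ULN is an assumption. Baseline may enter through the scale itself. Even under ULN anchoring, saturation is confined to the any-grade row, because the share above 3x ULN moves with the ALT course. This objection stands, and the ALT figures are therefore conditional.

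A reader might also infer that the SAP dropped a baseline comparison the protocol had promised. The protocol supplied says that, when no pre-treatment value exists, "the baseline value will be assumed to be normal (ie, no grade [Grade 0]) for the summary of graded laboratory abnormalities". That is section 9.4.5 of the THRIVE protocol, a different sub-study, which excludes ALT above ULN. The SAP is based on the STRIVE protocol and the Master Protocol, neither of which is supplied. Nothing shows that STRIVE text was dropped.

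The stakes are also limited. Section 4.7 makes all safety analysis descriptive, so no formal cohort comparison rests on this table. Baseline ALT is summarized by cohort (4.2.2). Change from baseline, ALT ≤ ULN proportions with confidence intervals, individual ALT plots, listings and the ECI are all planned (4.4.1, 4.7.4.1, 4.7.5).

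What survives is the rule itself: worst post-baseline grade, no stated worsening requirement, no shift table. The other outputs fill this only in part. Visit-level change in cohorts of about 10 to 15 does not show each participant's worst excursion, and the ALT ≤ ULN proportions and ALT plots have no counterpart for the other Appendix 5 parameters.

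**Conclusion.** The point holds as a minor improvement to one descriptive safety table. As written, 4.7.4.2 counts a pre-existing abnormality that persists as an on-treatment one, for any Appendix 5 parameter graded on absolute limits. For ALT, the any-grade count with no drug effect over 14 samples is about 100% if grades are anchored to ULN and 2-63% if anchored at 1.5x baseline. Which applies turns on cut-offs the SAP does not print. Both figures rest on the assumed entry distribution and within-person SD.

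It would be tempting to conclude that hepatic safety cannot be read from the planned outputs. That does not follow, given the baseline-aware ALT outputs already in the SAP.

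**What to change.** In 4.7.4.2:
- Make the main count treatment-emergent: a post-baseline grade in the TE period at least one grade above the baseline grade.
- State how an abnormal baseline is graded under the cited scale, and how a missing baseline is graded (for example as Grade 0).
- Add a table of baseline grade by worst post-baseline grade for each Appendix 5 parameter, by cohort.
- Keep the current worst-grade count as a secondary display.

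The cost is SAP text, one derived flag and one table shell, using data already collected. A one-grade rule does not remove within-person variation: on the assumed inputs with ULN cut-points, it still flags 20-57% for ALT over 14 samples with no drug effect. The shift table matters for that reason, since it shows where each participant started.

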4.7.5. Summaries of Events of Clinical Interest

The TE laboratory events of clinical interest (ECI) are defined as instances of:

- ALT > 5 x ULN and > 2 x baseline.

The number and percentage of participants with ECI will be summarized for each scheduled visit until EOS by cohort. If any participant has multiple ECIs, they will only be counted once. An ECI is considered resolved when ALT returns to \leq Day 1 baseline value.

A listing including individual participant ECI data will be provided.

If a participant has at least one ECI, the related data – substance use, exercise, and travel history – will be collected, and the corresponding listings will be presented. Otherwise, if no participant meets the ECI criteria, the three listings will not be provided, as no data will have been collected.

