1.2.5. NRTI Retreatment

It is recommended that NRTI therapy be reinitiated in participants during the Follow-Up Period if they meet any of the following criteria:

- HBV DNA increase $\geq 2 \log_{10}$ IU/mL within a 2-week period
- HBV DNA $> 100,000$ IU/mL at any Follow-Up Period visit (regardless of other biochemical parameters or ALT values)
- Confirmed increase of HBV DNA $> 20,000$ IU/mL (i.e., at 2 consecutive collections, regardless of other biochemical parameters or ALT values)
 - Note: The repeat HBV DNA test should be performed as soon as possible and no later than 7 calendar days after the initial result is received. Central laboratory testing is preferred, but local laboratory results will be accepted if it is not feasible to collect central laboratory results in time.

- HBV DNA > 2,000 IU/mL concurrent with any of the following criteria at the same visit:
 - Confirmed total bilirubin > 2x ULN and ALT > ULN
 - Any sign of hepatic decompensation (including, but not limited to, confirmed increase in prothrombin time [PT] ≥ 2 or international normalized ratio [INR] ≥ 0.5 from baseline, jaundice, ascites, encephalopathy, etc.)
 - ALT > 10x ULN
 - ALT > 2x ULN persisting for ≥ 12 consecutive weeks
 - ALT > 5x ULN persisting for ≥ 4 consecutive weeks
- Confirmed HBeAg seroreversion (i.e., HBeAg positive after being HBeAg negative at NRTI discontinuation)
- Any other clinically significant event(s) warranting initiation of NRTI therapy in the opinion of the investigator after discussion with the Sponsor

Participants who are retreated with NRTI therapy should continue to be followed per the SOA for the Follow-Up Period through the Week 48 visit. Participants with HBV DNA increase $\geq 2 \log_{10}$ IU/mL within a 2-week period should:

[figure not shown]
[figure not shown]
- return to the site for an unscheduled visit to measure HBV DNA levels and liver function tests as soon as possible after the investigator becomes aware of the HBV DNA increase
- continue returning weekly until HBV DNA levels stabilize (do not increase $\geq 1 \log_{10}$ IU/mL over a 4-week period or start decreasing for at least 2 consecutive visits), after which they should continue per the SOA for the Follow-Up Period

If any unscheduled visits needed as outlined above coincide with an existing visit per the Follow-Up Period SOA, then the Follow-Up visit assessments should be conducted.

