For event/measurement occurring on or after Day 1, the study day will be calculated as:

$$\text{Study Day} = (\text{Date of event/measurement} - \text{Date of first study drug administration}) + 1.$$

End of treatment (EOT) date: EOT date is the date of the last dose of VIR-2218, VIR-3434 and PEG-IFNa.

EOT assessment: The earliest available assessment on or after EOT date.

EOT + 24 weeks assessment: The earliest available assessment on or after EOT + 161 days.

Treatment Period and Follow-Up Period: Treatment Period and Follow-Up Period are defined in the protocol.

Treatment-emergent (TE) Period: The TE Period is defined as the time period on or from the start of study intervention(s) until the last dose of VIR-2218 + 30 days, or VIR-3434 + 24 weeks, or PEG-IFN α + 30 days, or TDF/TD + 30 days, whichever is later. The TE Period will be used for safety analysis.

Post-TE Period: The Post-TE Period is defined as the time period after the TE Period through the end of Follow-Up Period.

Analysis windows: The analysis window rules for protocol-defined visits are provided in [Appendix 2](#).

Unscheduled visits: Unscheduled visit measurements will be included in the analysis as follows:

1. In planned visit windows as specified, the analysis window rules described in [Appendix 2](#), if applicable.
2. In the derivation of the baseline.
3. In the derivation of maximum and minimum values, or maximum and minimum change from baseline values during the Treatment Period and Follow-Up Period for efficacy analyses, or worst values/grades during the TE Period for safety analyses.
4. In individual participant data listings as appropriate.

Repeated observations: Measurements recorded at different time points are defined as repeated observations. If an assessment has planned repeated measurements, then statistical summaries will present all planned time points, as appropriate.

If there are multiple records at a single assessment date, regardless of whether scheduled or unscheduled visit, the latest record will be used for the analysis.

Missing data handling conventions:

- Missing data can occur due to study withdrawal or participants lost to follow-up before the completion of the study or due to intermittent missing values (i.e., data between two non-missing assessments).
- Missing data in the by-participant data listings will be presented as missing.

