APPENDIX 2. ANALYSIS WINDOWS FOR STUDY ASSESSMENT

Notes:

- The analysis windows will be applied using the following rules for both scheduled and unscheduled visits:
 - a. If no numerical measurement is available within an analysis window, the measurement will be considered missing for the visit.
 - b. If there is more than 1 numerical measurement available within an analysis window, use the following rules:
 - i. The scheduled visit measurement will be used if it is available;
 - ii. The unscheduled visit measurement closest to the target day will be used unless the scheduled visit is available; or
 - iii. If there are multiple unscheduled visit measurements at the same distance from the target day, the latest measurement will be used.
- For the study assessments, e.g., laboratory, ECG, and vital sign measurements, collected on the date of the first dose of study drug, the following rules will be applied if it cannot be determined whether the measurement is before or after the first dose:
 - a. Scheduled measurement will be treated as a pre-dose observation.
 - b. Unscheduled measurement will be treated as a post-dose observation.
- Analysis Visits: The visit name for analysis purpose is used to report data in tables and figures.
- The Analysis Window is continuous, without leaving any date gaps between visits (no gap date). The Analysis Window boundaries are left exclusive, right inclusive, except specified otherwise.

Table 7: Analysis Windows for Safety, Efficacy, and other Assessments: Treatment Period for Cohort 1a/2a

Study Stage	Screening	Treatment Period												
Visit Week		W1	W4	W8	W12	W16	W20	W24	W28	W32	W36	W40	W44/ EOT	
Visit Day ± Visit Window	D -56 to -1	D1	D8±2	D29±2	D57±2	D85±2	D113±2	D141±2	D169±2	D197±2	D225±2	D253±2	D281±2	D309±2
Analysis Visit	Week 1 Day 1 (Baseline)	Week 1 Day 8	Week 4	Week 8	Week 12	Week 16	Week 20	Week 24	Week 28	Week 32	Week 36	Week 40	Week 44 /EOT	
Analysis Window	< D1 dose time	≥D1 dose time, +7	±14	±14	±14	±14	±14	±14	±14	±14	±14	±14	-14, EOT Date	
HBsAg quantitative, HBV DNA quantification, Liver function tests, Serum chemistry, Hematology, Coagulation parameters.														
Analysis Visit	Week 1 Day 1 (Baseline)		Week 4	Week 8	Week 12	Week 16	Week 20	Week 24	Week 28	Week 32	Week 36	Week 40	Week 44 /EOT	
Analysis Window	< D1 dose time		≥D1 dose time, +14	±14	±14	±14	±14	±14	±14	±14	±14	±14	-14, EOT Date	
Anti-HBs quantitative, HBeAg quantitative, HBcrAg, HBV RNA.														

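### The only ECI table is by scheduled visit: it can miss an ALT event seen only at an unscheduled visit, and no table counts participants who ever had one

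*SAP*

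**What the plan says.** SAP 4.7.5 defines an ECI as "ALT > 5 x ULN and > 2 x baseline". The planned table is: "The number and percentage of participants with ECI will be summarized for each scheduled visit until EOS by cohort". Two further sentences follow: "If any participant has multiple ECIs, they will only be counted once" and "A listing including individual participant ECI data will be provided". No row for an ECI at any time is named. The section calls the events treatment-emergent but carries the table to end of study.

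SAP 4.1 says how unscheduled values are used. Item 1 of its list admits them "In planned visit windows as specified, the analysis window rules described in" Appendix 2. For a window with more than one value, Appendix 2 says "The scheduled visit measurement will be used if it is available", and then "The unscheduled visit measurement closest to the target day will be used unless the scheduled visit is available". Item 3 of the same list admits unscheduled values to worst values or grades in the TE Period for safety analyses. SAP 4.7.4.2 plans a worst-grade laboratory table on the CTCAE scale, with ALT among its parameters (Appendix 5). SAP 4.7.4.1 lists liver tests from scheduled and unscheduled visits alike.

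Unscheduled liver tests are part of the plan. Under SAP 1.2.5, a participant whose HBV DNA rises by at least 2 log10 within two weeks should "return to the site for an unscheduled visit to measure HBV DNA levels and liver function tests as soon as possible", and then come back weekly until HBV DNA stabilizes.

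**The concern.** The figure a reader of the hepatic safety results wants first is how many participants in each cohort had an ECI. The planned table answers a different question: how many qualified at each scheduled visit, after the window rule has chosen one value per window. The rule makes no reference to size, so it can keep a normal scheduled ALT and pass over a qualifying unscheduled one a week later.

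The plan itself generates such values, because it calls participants in for extra liver tests when HBV DNA is rebounding. The counting sentence adds a second difficulty. It has no unit, so two programmers could build different tables from the same data.

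**Working it through.** No figure in the plan needs reproducing here. The check traces the window rule and then sizes the effect of one masked participant. It uses the SAP alone. That SAP is written for STRIVE, whereas the protocol supplied is for THRIVE, which has a different ECI definition (ALT > 3 x ULN).

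**Step 1: window widths.** These apply to HBV DNA, HBsAg and liver tests (Appendix 2, Tables 11 to 13; left bound exclusive, right bound inclusive).

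| Participants | Follow-up visits | Window | Width |
|---|---|---|---|
| Stop NRTI at F1 (Table 12) | F4 to F10 | ±7 | 14 days |
| Stop NRTI at F1 (Table 12) | F16 to F48 | ±14 | 28 days |
| Stop NRTI at F12 (Table 13) | F14 to F22 | ±7 | 14 days |
| Stop NRTI at F12 (Table 13) | F28 to F48 | ±14 | 28 days |
| Never stop NRTI (Table 11) | F24, F36, F48 | -14/+42, ±42, -42/+14 | 56, 84, 56 days |

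With weekly draws, a 14-day window holds 14/7 = 2 values and a 28-day window holds 28/7 = 4. Each width exceeds the weekly interval, so a scheduled and an unscheduled ALT can share a window.

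**Step 2: trace of the rule.** The ALT series are hypothetical. Assume baseline ALT of 2 x ULN, so the criterion is ALT > 5 x ULN and > 2 × 2 = 4 x ULN; the first condition binds. The participant stopped NRTI at F1. The F28 window is Day 197 ± 14, that is Days 184 to 211. F32 is targeted at Day 225.

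- Case A: scheduled ALT 1.8 x ULN on Day 197; unscheduled 7.0 on Day 204 and 6.0 on Day 211; scheduled 1.5 on Day 225. The F28 window keeps 1.8 and F32 shows 1.5. By-visit table: 0 ECIs. Any-time count: 1.
- Case B: the same flare with no scheduled F28 value. The unscheduled value closest to the target day is 7.0 (Day 204), so the ECI is counted at F28.
- Case C: scheduled 6.5 at F28 and 5.5 at F32. The participant is counted in both rows if the unit is the visit. If the unit is the study, only one row gets the count, and no rule says which.

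**Step 3: reach of the worst-grade table.** The TE Period ends at the latest of VIR-3434 + 24 weeks and 30 days after the last dose of each other drug (SAP 4.1). Assume VIR-3434 ends at EOT and no TDF/TD is taken after it is stopped.

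- Stop at F1: TDF/TD limit is 7 + 30 = 37 days after EOT. The VIR-3434 limit, 24 × 7 = 168 days, governs.
- Stop at F12: TDF/TD limit is 84 + 30 = 114 days. 168 days governs again.

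The worst-grade table therefore covers 24 - 1 = 23 off-NRTI weeks for an F1 stopper and 24 - 12 = 12 for an F12 stopper. It leaves out the last 48 - 24 = 24 weeks of follow-up for both. Case A falls in that later half. A participant who never stops TDF/TD stays in the TE Period throughout follow-up.

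**Step 4: size of one masked participant.** Planned cohort sizes are about 10 (1a, 2a, 3a) and about 15 (4a, 5a), from SAP 1.2.2.

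- 1/15 = 6.7 percentage points; 1/10 = 10 percentage points.
- Illustration with an assumed 3 ECI participants of 15: 3/15 = 20.0% becomes 2/15 = 13.3% if one is masked.

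**The case against.** The other side has several sound points.

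- **The data are not lost.** The ECI listing, the liver-test listings and the TE-Period worst-grade table all keep the event visible, and in cohorts of 10 to 15 a listing can be read line by line. This stands, and it limits the harm to one table's count. But a listing gives no incidence, CTCAE grade is not the ECI criterion, and the worst-grade table stops at the end of the TE Period.
- **The SAP may intend worst values here.** SAP 4.1 item 3 could be read as bringing unscheduled ALT into the ECI derivation. That is possible, but 4.7.5 is laid out by scheduled visit and does not say so; item 3 is also confined to the TE Period.
- **An ECI stays open until ALT returns to the Day 1 value**, so an unresolved event might be counted at the next scheduled visit. Section 4.7.5 does not say that its rows count ongoing events. In Case A it would not help, because 1.5 x ULN is already below the baseline of 2.

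A reader might also infer three stronger things that the documents do not support.

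- **That flares at unscheduled visits drop out in general.** They do not: Case B is counted, and so is a flare that lasts to a scheduled draw.
- **That counting a participant once contradicts a by-visit table.** Once per visit row fits that layout. What is missing is the unit.
- **That 75% of such events would be missed**, because 3 of 4 weekly draws in a 28-day window are unscheduled. That needs an exceedance at exactly one draw. With a 14-day window the same reasoning gives 1/2, and a flare covering all four weekly draws is never missed. The early off-NRTI windows are mostly about 14 days, and only a rapid HBV DNA rise triggers the weekly visits.

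**Conclusion.** The point holds as a gap in the ECI summary. Followed as written, the SAP can leave a participant with a genuine ECI out of its only ECI table, under one condition: a non-qualifying scheduled ALT in the same window as the qualifying unscheduled one. No planned table reports how many participants ever had an ECI, the counting unit is unstated, and the period is unclear because events labelled TE are tabulated to end of study.

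Each masked participant costs 6.7 to 10 percentage points at the planned cohort sizes of 15 to 10; floater participants added to a cohort would make the step smaller. The frequency of masking depends on how long flares last and on window width, and the documents give no basis for estimating it. The finding assumes that the by-visit rows follow Appendix 2, which is what SAP 4.1 item 1 directs. It concerns the reporting of safety data only and does not suggest that any event would go unrecorded.

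**What to change.** In SAP 4.7.5:

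1. Add a summary, by cohort, of the number and percentage of participants with one or more ECIs at any post-baseline central-laboratory ALT, scheduled or unscheduled. Count each participant once within each of three rows: TE Period, post-TE Period and overall.
2. State that the by-visit rows are a prevalence display, in which a participant counts once at each visit where the criterion is met by the value chosen under Appendix 2.

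The first change supplies the missing incidence and settles the period; the second settles the counting unit. The cost is two sentences and a few table rows, from data already collected. Local-laboratory ALT would remain in listings only, as SAP 4.1 already provides.
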